- Patients with active cancer within 2 months of the study
- Patients with pharyngocutaneous fistula
- Vulnerable population:
 - Adults unable to consent
 - Individuals who are not yet adults (infants, children, teenagers)
 - Pregnant women
 - Prisoners

5) Study Timelines

The subjects will be in study from the time they sign the consent form to completion of the videofluoroscopy study. Approximately 5 additional minutes will be added to each subject's clinical DSS study, with no more than 1-2 seconds of additional fluoroscopic exposure. The estimated date of complete of the study will be 12 months after IRB approval.

6) Study Endpoints

Primary endpoint of the study is complete videofluoroscopic data for all 10 patients.

7) Procedures Involved

Each subject will undergo a standard DSS for the purpose of medical diagnosis. The research study portion will be incorporated into the procedure for patients who consent to participation in the study. The dynamic swallow study is a radiologic examination of swallowing function using fluoroscopy. Standard examinations consist of multiple radio-opaque boluses of different consistencies. During a standard videofluoroscopic study, subject are asked to

PROTOCOL TITLE: Utilization of Continuous Positive Airway Pressure to Improve Swallow Function in Patients Post Total Laryngectomy

swallow barium-coated foods of the following volumes and consistencies in side and front view. Swallows can be added to the protocol in order to assess clinical questions relevant to each specific patient.

Lateral Plane

- 1 ml liquid barium (X2)
- 20 ml liquid barium (X2)
- 60 ml thin liquid barium consecutive sips via straw
- 3 ml pudding

Anterior-to-Posterior Plane

- 20 ml liquid barium
- 13 mm barium tablet

In order to minimize exposing participants to additional radiation during this study, the patients will be asked to wear the CPAP mask during standard swallows test for one of the two swallows of the following consistencies in side view:

- 1 ml thin liquid barium
- 20 ml thin liquid barium

One additional 3ml pudding bolus swallow with the CPAP mask will be added in order to compare swallow function of a pudding consistency with and without the CPAP. This additional swallow will add no more than 1-2 seconds of videofluoroscopic exposure time.

8) Data and/or Specimen Management and Confidentiality

The measures explained in the online application will be taken to protect the confidentiality of subjects:

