Videofluoroscopic data collected from the above protocol will be analyzed by paired sample T test and repeated measures of analysis of variance. Data will be stored anonymously and securely, accessible with a password available only to participating researchers.

9) Data and/or Specimen Banking

N/A

PROTOCOL TITLE: Utilization of Continuous Positive Airway Pressure to Improve Swallow Function in Patients Post Total Laryngectomy

10) Provisions to Monitor the Data to Ensure the Safety of Subjects

N/A. This study does not pose more than a minimal risk to subjects.

11) Withdrawal of Subjects

Subjects unable to complete the entire protocol may be withdrawn from the study and not included in data analysis.

12) Risks to Subjects

Patients are undergoing the videofluoroscopic procedure as standard of care. One additional swallow will be added to the standard protocol, adding a minimal 1-2 seconds of fluoroscopic exposure time.

The risks of the CPAP device include skin irritation, dry mouth, nasal congestion. These risks are unlikely to occur during this study in which patients will be wearing the mask for only several minutes. Subjects may experience stomach bloating. Subjects may experience discomfort from wearing the mask.

13) Potential Benefits to Subjects

No direct benefit to participating subjects is anticipated.

14) Multi-Site Research

N/A

15) Sharing of Results with Subjects

Results will not be shared with subjects.

16) Prior Approvals

Radiation Use Committee approval was obtained before IRB submission

17) Provisions to Protect the Privacy Interests of Subjects

Subjects will undergo the protocol privately with a limited number of qualified personnel present. Beyond determining eligibility as described above, no personal or medical information will be sought from participants. The procedure will be limited to only what is described in the above protocol. Only qualified research personnel working on the project will access subjects' secure data, which will be password-protected.

PROTOCOL TITLE: Utilization of Continuous Positive Airway Pressure to Improve Swallow Function in Patients Post Total Laryngectomy

18) Compensation for Research-Related Injury

N/A. The study procedure does not pose more than minimal risk to subjects.

19) Economic Burden to Subjects

N/A

20) Drugs or Devices

N/A

References

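### The protocol describes no concealment of CPAP condition when the films are measured, so reader expectation could enter the paired efficacy comparison

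*Combined protocol and SAP*

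**What the plan says.** The objective (Section 2) is an efficacy question: whether CPAP improves swallowing after total laryngectomy. The background (Section 3) gives the expected direction, namely that added pressure may help move the bolus.

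Section 7 sets up the comparison within each patient, during one examination. For the 1 ml and 20 ml liquids, patients "wear the CPAP mask during standard swallows test for one of the two swallows of the following consistencies in side view". For pudding, "One additional 3ml pudding bolus swallow with the CPAP mask will be added in order to compare swallow function of a pudding consistency".

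The whole analysis plan is one sentence in Section 8: "Videofluoroscopic data collected from the above protocol will be analyzed by paired sample T test and repeated measures of analysis of variance". The next sentence deals with storage: "Data will be stored anonymously and securely, accessible with a password available only to participating researchers". Section 17 adds, under privacy, "Only qualified research personnel working on the project will access subjects' secure data, which will be password-protected".

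Section 6 defines the endpoint as completeness of data: "Primary endpoint of the study is complete videofluoroscopic data for all 10 patients".

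The protocol names no swallow measurement and no reader. It mentions no coding of clips, reading order, independent reader or second reader.

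**The concern.** Swallow results have to be extracted from moving images. Even a timing measure usually requires someone to choose a start frame and an end frame. A reader who knows both the condition and the hypothesis may make those choices slightly differently for the two conditions, without intending to.

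Condition is the contrast being tested within each patient. A reading shift tied to condition therefore passes in full into the paired difference. Neither the paired t test nor the repeated-measures ANOVA can separate it from a real effect of CPAP.

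Patients and staff in the room can hardly be kept unaware of a face mask. Concealment at the reading stage is the protection still available, and the protocol does not mention it. What is at stake is how far an apparent benefit on the efficacy objective could be trusted.

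**Working it through.** **Step 1: does any section supply concealment?**

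- Section 7 describes how swallows are recorded, not how films are read.
- Section 8 states the tests. Its promise of anonymous storage protects patient identity; it does not hide whether a swallow was made with CPAP.
- Section 17 restricts access to the project team. That makes project readers a strong inference, but it does not say whether they know the condition.
- Section 8 also points to measures in an online application, which is not among the documents. It is cited for confidentiality only.

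Concealment is therefore not described, and open reading is permitted but not stated.

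**Step 2: what would a reader shift do?** The plan has no figure to reproduce, because it gives no significance level, effect size, SD or reader-error estimate.

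Inputs:
- n = 10 patients (Section 6).
- Paired t test (Section 8), so df = 10 − 1 = 9.
- Assumed: two-sided 5% level, giving a critical value of 2.262.
- Assumed: no true CPAP effect.
- Assumed: a systematic shift b toward CPAP, in units of the SD of the paired difference.

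Under these assumptions the test statistic follows a noncentral t distribution with 9 df and noncentrality b × √10. The chance of a significant result favouring CPAP is P(T > 2.262).

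| Assumed shift b (SD) | Noncentrality b × √10 | Chance of significant pro-CPAP result |
|---|---|---|
| 0 | 0 | 2.5% |
| 0.1 | 0.316 | 4.7% |
| 0.2 | 0.632 | 8.2% |
| 0.3 | 0.949 | 13.4% |
| 0.5 | 1.581 | 29.3% |

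Relative to 2.5%, shifts of 0.3 and 0.5 SD multiply the chance by about 5 (13.4 / 2.5) and 12 (29.3 / 2.5).

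**Step 3: is the small sample the cause?** No. The noncentrality grows with √n, so a fixed shift becomes significant more often in a larger trial. At n = 20 (df = 19, critical value 2.093), a 0.3 SD shift has noncentrality 0.3 × √20 = 1.342 and gives about 25%, against 13.4% at n = 10. The remedy has to be at measurement.

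**Step 4: size of the reading task.** 10 patients × 3 bolus types × 2 conditions = 60 clips.

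**The case against.** The strongest reply is that silence is not a procedure. A reader might infer that the team will read each patient's CPAP and no-CPAP films in sequence, knowing which is which. The documents do not support that: they name no reader, no order and no state of knowledge. A privacy rule that limits access to the project does not rule out a blinded reader within it. This part of the reply stands, so the point is confined to what the plan permits.

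Second, no outcome is named, so how far the readings depend on judgement is unknown. This also stands, and it is why the size of any bias cannot be established. It does not remove the point, since an unspecified measure leaves the reader more discretion rather than less. Defining the outcome is the more basic need.

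Third, the shifts of 0.2 to 0.5 SD are not drawn from any document. That is correct. The table shows what such shifts would do, not that they are likely.

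Fourth, the stated endpoint is completeness of data, which reader expectation does not affect. True, but both planned tests serve the efficacy objective, and that is where a shift would act.

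Fifth, concealment may fail. The documents do not say whether the CPAP mask appears on the lateral film, whether cropping would remove it, or whether cropped clips would remain measurable. A reader who attended the sessions might also recognise one of only 10 patients. These limits are real and have to be reported, but partial concealment is still better than none.

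**Conclusion.** The concern holds as an omission. The protocol describes no concealment of condition at film reading, and its access rules point to readers who know the expected direction. A shift toward CPAP, if it occurred, would pass undetected into the paired t test and the ANOVA. The Step 2 probabilities rest on the assumed two-sided 5% level, a true effect of zero and assumed shift sizes; the documents fix none of these.

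A reader might go further and conclude that a positive result could not be attributed to CPAP at all. The documents do not support that: no bias has been shown, and its size would depend on measures not yet named. Nor would blinded reading alone secure attribution. Section 7 gives no rule for which of the two liquid swallows is made with CPAP, and the CPAP pudding swallow is an added one, so order effects could remain.

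This is a worthwhile, inexpensive improvement to the efficacy comparison. It is not a defect in the stated endpoint.

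**What to change.** Add the following to Section 8, once the swallow measurements have been defined:

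- Before measurement, export each study swallow as a separate clip, strip overlays, and crop it as far as the landmarks needed for measurement allow.
- Give each clip a random code and shuffle the clips across patients and conditions.
- Have an existing team member, preferably one not present at the sessions, measure all coded clips.
- Join the key that links code to patient and condition only after the measurements are locked.
- State in the report how many clips still revealed the condition.

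The cost is preparing about 60 clips, someone to hold the key, and a lock step before analysis. It needs no added swallow, radiation or patient contact. Because it applies to recorded films, it can be adopted at any time before measurement is complete.

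If it removes the differential shift completely, the chance of a false pro-CPAP result on one paired test returns to the nominal 2.5%. The downside is that concealment may be only partial, if the CPAP mask stays in view or the reader recalls a patient. The change does not deal with order effects, which need their own provision.

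### Section 11 lets a whole subject be left out of the analysis when one swallow fails, so completed CPAP/no-CPAP pairs can be lost from their own paired tests

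*Combined protocol and SAP*

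**What the plan says.** Section 11 is one sentence: "Subjects unable to complete the entire protocol may be withdrawn from the study and not included in data analysis". It gives a trigger and a permission. It does not say when the permission is used, whether that is settled before the films are measured, or that numbers and reasons are reported. Section 5 ("The subjects will be in study from the time they sign the consent form to completion of the videofluoroscopy study") bounds participation, not exclusion of data.

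Section 7 produces three CPAP/no-CPAP pairs in side view. One of the two 1 ml swallows and one of the two 20 ml swallows is taken with the mask, and a masked 3 ml pudding swallow is added to the standard one. Three other listed tasks have no masked counterpart: "60 ml thin liquid barium consecutive sips via straw", the front-view 20 ml swallow, and "13 mm barium tablet".

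Section 8 says the data "will be analyzed by paired sample T test and repeated measures of analysis of variance", with no analysis set or missing-data rule. The primary endpoint in Section 6 is "complete videofluoroscopic data for all 10 patients". No section says whether a withdrawn subject is replaced.

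**The concern.** The exclusion acts on the subject, while the evidence comes in pairs. A subject who completes the 1 ml and 20 ml pairs but not the pudding pair has given everything the 1 ml and 20 ml paired t tests need. Removing that subject discards observed data for a reason unrelated to whether those data are usable.

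Two things are at stake. The first is precision, which matters with ten subjects. The second is bias: if those who stop are those who respond differently to CPAP, a comparison that was fully observed becomes a selected one. Section 12 names mask discomfort and stomach bloating, so stopping linked to CPAP is conceivable. Because the choice is optional and no reasons need be reported, a reader of the results could not tell whether this had happened.

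**Working it through.** **Plan's own figure.** The only number is 10 patients. It cannot be reproduced, because no significance level, power, effect size, SD or dropout rate is given.

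**What one failure can remove.** Section 7 lists 8 standard swallows, and the added masked pudding swallow makes 9. Three pairs use 6 of them, leaving 3 unpaired.
- Narrow reading (research swallows only): failing one pair can remove the other two completed pairs. Section 7 supports this reading by separating out a research part: "The research study portion will be incorporated into the procedure for patients who consent to participation in the study".
- Broad reading (the full swallow study): failing an unpaired task could remove all three completed pairs. Section 7 lends this some support: "Swallows can be added to the protocol in order to assess clinical questions relevant to each specific patient".

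The problem exists on either reading.

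**Precision.** Assumptions: SD of paired differences 1, two-sided 5% paired t test. Half-width = t(0.975, n-1)/√n. Power at a true difference of 1 SD comes from the noncentral t with n-1 degrees of freedom and noncentrality √n.

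| n analysed | Half-width (SD) | Power at 1 SD |
|---|---|---|
| 10 | 2.262/3.162 = 0.715 | 80.3% |
| 8 | 2.365/2.828 = 0.836 | 68.1% |
| 12 | 2.201/3.464 = 0.635 | 88.3% |

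If two of ten are dropped and not replaced, the 1 ml test moves from the first row to the second. If 12 are enrolled to obtain 10 completers, it stays at the first row, but keeping all 12 completed 1 ml pairs would give the third.

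**Bias.** Further assumptions: no true effect; positive differences favour CPAP; the pudding pair is missing in 2 of 10 subjects, who are dropped whole; pairs within a subject correlate ρ; the two are those lowest on a score that correlates r with the pudding difference. Dropping the two lowest of ten on the pudding difference itself moves the mean pudding difference of the remaining eight by 0.318 SD (simulated). Under joint normality the shift in the completed 1 ml comparison is ρ × r × 0.318. With ρ = 0.5, set beside 200,000 simulated trials per case:

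| r | Formula | Simulated bias (SD) | Chance of a false favourable result |
|---|---|---|---|
| 1 | 0.5 × 1 × 0.318 = 0.159 | 0.161 | 6.5% |
| 0.5 | 0.5 × 0.5 × 0.318 = 0.080 | 0.081 | 4.1% |
| 0 | 0 | 0.002 | 2.5% |
| -0.5 | -0.080 | -0.077 | 1.6% |

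At r = 1, ρ from 0.3 to 0.7 gives 0.3 × 0.318 = 0.095 to 0.7 × 0.318 = 0.223 (simulated 0.096 to 0.221). At ρ = 0 the bias is 0. With 12 enrolled and 2 dropped, r = 1 and ρ = 0.5 still give 0.138 SD (6.4%), so replacement restores n without removing the bias. If every completed 1 ml pair is kept, the bias is 0 and the error rate 2.5% in all these cases.

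**The case against.** Section 11 permits exclusion and does not require it. The session adds about five minutes with a mask worn briefly, so non-completion may be rare. The bias needs several links in a chain: a subject stops, the option is used, stopping is related to CPAP response, and pairs correlate within a subject. No passage supplies a rate or a link. Section 6 may mean ten completers, in which case n does not fall. A classical repeated-measures ANOVA across consistencies drops incomplete subjects anyway. All of this stands, and it limits the size of the point. None of it justifies removing a completed pair from its own paired t test.

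A reader might infer that failing the tablet or a patient-specific extra swallow removes a subject. That is possible but the weaker reading: Section 12 applies the label of standard protocol to the clinical examination, which suggests that Section 11 means the study's own procedures.

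**Conclusion.** The point holds in limited form. The plan allows completed, valid pairs to be dropped from the planned paired tests because another swallow failed, and requires no account of why. It should be fixed, but it does not undermine the design.

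Under the assumptions shown (2 of 10 dropped, ρ = 0.5, r from -0.5 to 1), the bias in a fully observed comparison lies between -0.08 and +0.16 SD, and is 0 if stopping is unrelated to response. The precision loss (half-width 0.72 to 0.84 SD, power 80% to 68%) does not depend on the mechanism but does depend on no replacement.

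A reader might go further and infer that Section 11 inflates the CPAP effect, perhaps by the 0.32 SD (18.7% chance of a false favourable result) that follows if the two worst responders in a comparison are dropped although their pairs were complete. The documents do not support that. Nothing links non-completion to poor response, and the direction of any bias is unknown. Bias in a pair that is itself missing comes from the missing data, not from Section 11.

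**What to change.** In Section 11, replace the closing clause on exclusion from analysis with:

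> Every completed CPAP/no-CPAP pair is analysed for its own consistency by the planned paired t test, whether or not other swallows were completed, except where a subject withdraws consent for use of data. Any exclusion is decided and documented before the films are measured. The number of, and reason for, every missing or stopped swallow are reported for all consented subjects.

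In Section 8, add that a classical repeated-measures ANOVA across consistencies uses only subjects complete for all pairs, is reported with its own n, and is secondary to the per-consistency paired tests. Without this line, Section 11 alone would not settle what happens in the ANOVA: with two pudding pairs missing, listwise deletion cuts its CPAP error degrees of freedom from 9 to 7. A pooled model is not needed for this point. If one is wanted, name a single model: paired differences with consistency fixed and patient random.

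The cost is wording in two sections and a record of the reason for each missing swallow, with no added procedures or radiation. The number of subjects may differ by consistency and must be shown, and the estimate may be less favourable to CPAP. Bias in a consistency whose own pair is missing is not removed.

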Official Title of Study: CPAP to Improve Swallow Function Post Total Laryngectomy

NCT# 03328702

Document Date May 20, 2016

Attached is the UC Davis IRB approved Protocol and there have been no protocol changes since 2016.

Sincerely,

A handwritten signature in black ink, appearing to read "[name]".

[name]., M.P.H., Ph.D.

Department of Otolaryngology Head and Neck Surgery

University of California, Davis School of Medicine

PROTOCOL TITLE: Utilization of Continuous Positive Airway Pressure to Improve Swallow Function in Patients Post Total Laryngectomy

1) Protocol Title

Utilization of Continuous Positive Airway Pressure to Improve Swallow Function in Patients Post Total Laryngectomy

Version date: 5.3.16

2) Objectives

To determine whether use of Continuous Positive Airway Pressure (CPAP) can improve the swallow function in patients who underwent total laryngectomy and are experiencing difficulty swallowing.

3) Background

Total laryngectomy is a procedure that involves surgical removal of the larynx and separation of the digestive and airway tracts. The procedure is typically conducted for cases of laryngeal cancer and intractable aspiration. Following this procedure, patients are no longer at risk for aspiration; however some patients continue to experience difficulties in propulsion of food or drink throughout the pharynx. These difficulties can result from pharyngeal neuromuscular damage caused by surgery and radiation (1). Previous research has demonstrated a reduction in pharyngeal contractile pressure and increased pharyngeal transit time in patients post laryngectomy (2,3). Continuous Positive Airway Pressure (CPAP) may assist bolus propulsion in these patients by increasing pressure in the direction of bolus flow. This study aims to evaluate the utility of a CPAP mask to improve pharyngeal swallow outcomes in patients with dysphagia following total laryngectomy. This specific population could be well-suited for this application, since the digestive tract and airway are completely separate and there is no risk of the aspiration into the airway.

PROTOCOL TITLE: Utilization of Continuous Positive Airway Pressure to Improve Swallow Function in Patients Post Total Laryngectomy

4) Inclusion and Exclusion Criteria

Inclusion criteria:

- Age \geq 18 years.
- Patients at least 2 months after total laryngectomy undergoing a dynamic swallow study (DSS).

Exclusion criteria:

- Patients with 100% neopharyngeal stenosis

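### Section 11 lets a whole subject be dropped from the analysis for failing any part of the protocol, which can bias the CPAP comparison in a direction that depends on which swallow failed

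*Combined protocol and SAP*

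**What the plan says.** The objective (Section 2) is "To determine whether use of Continuous Positive Airway Pressure (CPAP) can improve the swallow function in patients who underwent total laryngectomy". The target group is those who have dysphagia. Section 7 sets the comparison. For the 1 ml and 20 ml liquids in side view, "the patients will be asked to wear the CPAP mask during standard swallows test for one of the two swallows of the following consistencies". For pudding, "One additional 3ml pudding bolus swallow with the CPAP mask will be added in order to compare swallow function of a pudding consistency". That bolus, too, is therefore compared masked against unmasked.

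Section 8 gives the whole analysis plan: "Videofluoroscopic data collected from the above protocol will be analyzed by paired sample T test and repeated measures of analysis of variance". Section 6 reads: "Primary endpoint of the study is complete videofluoroscopic data for all 10 patients". Section 11 reads: "Subjects unable to complete the entire protocol may be withdrawn from the study and not included in data analysis". Section 12 includes: "Subjects may experience discomfort from wearing the mask", and also lists stomach bloating.

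The protocol does not say how the discretion in Section 11 is to be used, how an attempted but unfinished swallow is handled, whether withdrawn subjects are replaced, or whether the 10 patients in Section 6 are those enrolled or those who finished. It plans no sensitivity analysis and no reporting of withdrawals by reason.

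**The concern.** Whether a subject stays in the analysis depends on something that happens after the mask is applied and that the mask can influence. If a patient completes the unmasked swallow but cannot complete its CPAP partner, that is information about CPAP, yet Section 11 allows the patient to be left out. The paired test would then describe only patients in whom CPAP was workable.

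The rule is also broader than the comparison needs. A patient who completes all three pairs but fails an unrelated item, such as "60 ml thin liquid barium consecutive sips via straw", may lose all three pairs. With 10 patients, one or two such decisions matter. Because no criteria are given, they could be taken after the films have been seen.

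**Working it through.** **1. Which swallows can trigger exclusion.** Counting each line of Section 7 as one task per repetition gives 8 standard swallows (2 + 2 + 1 + 1 lateral, 2 anterior-to-posterior) plus 1 added pudding swallow, 9 in all.
- 3 with CPAP: 1 ml, 20 ml, pudding.
- 3 unmasked partners: 1 ml, 20 ml, pudding.
- 3 outside any pair: 60 ml sips, 20 ml front view, 13 mm tablet.

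On the natural reading of Section 11, failure at any of the 9 permits exclusion. Only the first 3 involve CPAP, and the last 3 do not enter the comparison at all.

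**2. The plan's own figure.** The 10 patients cannot be reproduced: no alpha, power, effect size, SD or dropout is stated. Everything below rests on assumptions.

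**3. Bias with replacement.** Assume CPAP-minus-no-CPAP differences D ~ N(0,1), positive favouring CPAP, no true effect, 10 completers, and a two-sided 5% paired t test (2.5% in favour of CPAP). A subject fails to complete when a standard normal variable, correlated ρ with D, falls in its lowest fraction p. The mean shift among completers is ρ·φ(z_p)/(1−p), with z_p = Φ⁻¹(p):
- p = 10%: 0.1755/0.9 = 0.195
- p = 20%: 0.2800/0.8 = 0.350
- p = 30%: 0.3477/0.7 = 0.497

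Each is multiplied by ρ, so at ρ = 0.5 the shifts are 0.10, 0.17 and 0.25 SD. Simulated rates of false claims for CPAP:

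| ρ | p = 10% | p = 20% | p = 30% |
|---|---|---|---|
| 0 | 2.5% | 2.5% | 2.5% |
| 0.3 | about 4% | about 5% | about 6% |
| 0.5 | about 5% | about 7% | about 11% |
| 1 (upper bound) | 7% | 20% | 49% |

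The last row requires that exactly the worst differences drop out and that those patients are replaced.

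**4. Direction, without replacement.** Take 10 subjects, no true effect, correlation 0.5 between the two conditions, and drop 1, 2 or 3 subjects:
- Worst CPAP swallows dropped: bias +0.09, +0.16, +0.23 SD; false claims for CPAP about 4%, 6%, 8%. Over correlations 0.3 to 0.7 the range is about 4% to 11%.
- Worst unmasked swallows dropped: bias −0.09, −0.16, −0.23 SD, the mirror image against CPAP.
- Worst swallow in either condition dropped: bias about 0; false claims about 2.5%.

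**5. Precision lost when completed pairs are discarded.** The standard error of the mean difference grows by √(10/n): √(10/9) = 1.05, √(10/8) = 1.12, √(10/7) = 1.20 for 1, 2 or 3 subjects dropped.

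**6. The completion endpoint.** If the 10 are those enrolled, the chance that all complete is (1−p)^10: 0.95^10 = 60%, 0.90^10 = 35%, 0.80^10 = 11%. If non-completers are replaced or leave the denominator, the endpoint is met by construction. As an illustration, 10/10 has an exact 95% CI of 69–100%, while 10/13 has 46–95%.

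**7. What a worst-rank analysis would cost.** Take 10 starters, a true benefit of 1 SD, and failures unrelated to effect at 10%, 20% or 30%. Power of the signed-rank test with failed CPAP swallows ranked worst is about 27%, 8% and 2%, against 74%, 67% and 59% for the t test on completed pairs. With no true effect on swallowing, the worst-rank test declares significant harm in about 6%, 13% and 25% of trials.

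**The case against.** A reader might infer that the plan removes failed CPAP swallows as missing and so biases the answer toward CPAP. The documents do not support that, for four reasons.
- Section 11 says that subjects may be excluded, not that they will be, and it does not mention CPAP.
- The rule reaches unmasked items too. Excluding patients who fail those biases against CPAP or has no net effect.
- A poor CPAP swallow that is filmed to its end is complete data and stays in. Only unfinished swallows are at issue.
- Mask intolerance need not mean worse bolus propulsion. Section 12 presents discomfort and bloating only as possibilities, with the mask worn for several minutes, so nothing in the documents supports non-completion as high as 20–30%.

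Nor can it be said that failures leave the completion endpoint. If the 10 are those enrolled, one non-completer makes it fail.

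All of this stands, and it limits the claim about direction and size. It does not rescue the rule. Permission without criteria is itself a weakness, exclusion still depends on an event that CPAP can cause, and nothing elsewhere in the protocol repairs it. The objection to worst rank as the main analysis also stands: it would answer a combined question about tolerability and function, at the power cost shown in step 7.

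**Conclusion.** The point holds as a risk whose direction depends on the reason for non-completion. Section 11 permits whole-subject exclusion at discretion, discards usable pairs, and can bias the paired comparison toward CPAP if masked swallows are the ones that fail.

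Under zero true effect, 10 completers with replacement and 10%, 20% or 30% non-completion, a moderate link (correlation 0.5) gives about 5%, 7% and 11% false claims for CPAP against 2.5% nominal. With no link there is no inflation. The 7%, 20% and 49% figures are a limiting case and should not be read as the expected effect. Replacement, the non-completion rates, the correlation and the 5% level are all assumptions. The rule should be changed because doing so is nearly free, not because a large bias has been shown.

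**What to change.** **Section 11.** Replace the closing clause, which takes these subjects out of the data analysis, with: all subjects who start the study swallows are included, and every bolus pair completed both with and without CPAP is analysed. This changes only the analysis. It does not alter when a subject may stop.

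**Section 6.** Report subjects completing all CPAP swallows over all subjects who started, with an exact 95% CI. List non-completions by condition (CPAP or no CPAP), bolus and reason.

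**Section 8.** Keep the paired t test on measured pairs as the main analysis. Add a sensitivity sign or signed-rank test in which an attempted but uncompleted swallow is ranked worst for its own condition, in either direction.

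**Limits and cost.** A pair with a failed swallow still has no measured difference, so the main analysis remains conditional on completing that pair. The listing and the sensitivity test make this visible but do not remove it. The worst-rank test mixes tolerability with function and can lose most of its power at 10–30% non-completion, so it should not replace the main analysis. Otherwise the cost is a few sentences and a short log of attempted and completed swallows, with no extra patients or fluoroscopy.
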